## **2.2 Research Questions**

- 1) Does the Active Women over 50 program increase daily steps in women aged 50+ years compared to waitlist control?
- 2) Does the Active Women over 50 program improve physical activity, mental wellbeing, physical function, quality of life, sleep, balance, action planning, and coping planning, and reduce bodily pain, menopause symptoms, fear of falling, and falls compared to waitlist control?
- 3) What are the participant's experiences of the Active Women over 50 program? What are the contextual factors that affect the program uptake and maintenance?
- 4) What is the cost-effectiveness of the Active Women over 50 program compared to waitlist control?
- 5) Is there potential for the Active Women over 50 program to be implemented and scaled up? What are the characteristics of implementation that would support scale up and sustainability?
- 6) What is the impact of the Active Women over 50 program on physical activity and other secondary outcomes 6 months after the program ending?

## **2.3 Rationale for Current Study**

Regular physical activity in younger years delays disability in women aged 70+ by up to 15 years, yet participation is sub-optimal. Mid-life physical activity is also associated with a higher likelihood of being physically active in older age. Women in middle age have unique barriers to becoming more active, such as multiple caring responsibilities and onset of chronic conditions, yet very few evidence-based, low-cost, scalable approaches to physical activity aim to reach a large proportion of them. Commencement of appropriate physical activity by women in their 50s should, therefore be a priority. We have designed an intervention to enhance physical activity participation in women aged 50+, which has been pilot-tested in a small sample and showed acceptability, uptake and positive recommendation. However, the promising impact observed on physical activity warrants further testing in a large trial.

## **3 STUDY OBJECTIVES**

### **3.1 Primary Objective**

The primary objective is to test the effectiveness of the Active Women over 50 program on average daily steps at 6 months compared with a waitlist control among women aged 50+.

### **3.2 Secondary Objectives**

Secondary aims are (1) to evaluate the effectiveness of the Active Women over 50 program on physical activity, falls, mental wellbeing, physical function, quality of life, sleep, bodily pain, menopause symptoms, balance, fear of falling, action planning, and coping planning at 6 months after randomisation; (2) to evaluate the effectiveness of the Active Women over 50 program on goal attainment at 6 months after randomisation; (3) to evaluate the proportion of participants who i) achieve light physical activity and lower limit MVPA/week, ii) increase their daily steps by 2000+ from baseline to 6 months after randomisation; (4) to explore the experiences of participants of the Active Women over 50 program and to investigate contextual factors that affect the program uptake and maintenance; (5) to assess the cost-effectiveness, implementation potential and determinants to guide scale-up from the perspective of the healthcare and community funder; (6) to test secondary implementation outcomes (reach, fidelity and adoption, dose, sustainability); (7) To evaluate the number of daily steps for intervention participants 6 months after the program has ended, at 12 months after randomisation; (8) to evaluate the effect of the Active Women over 50 program on physical activity, falls, mental wellbeing, physical function, quality of life, sleep, bodily pain, menopause symptoms, balance, fear of falling, action planning, and coping planning for intervention participants 6 months after the program has ended, at 12 months after randomisation; (9) to evaluate the proportion of intervention participants who i) achieve light physical activity and lower limit MVPA/week, ii) increase their daily steps by 2000+ from 6 to 12 months after randomisation.

## **4 STUDY DESIGN**

### **4.1 Type of Study and Participants**

This study will use a two-arm parallel pragmatic hybrid type I effectiveness-implementation randomised controlled trial (n=1000) to test the effectiveness of the Active Women over 50 program on daily steps at 6 months compared with wait-list control among women aged 50+. In addition, a process evaluation will be undertaken to explore the experiences of participants in the intervention group after completing the program through interviews of approximately 30 participants and the impressions survey completed by all intervention group participants at 6-month follow-up. An economic analysis will also be carried out to evaluate cost-effectiveness, considering the perspective of both healthcare providers and community funders. The impact of the Active Women over 50 program on physical activity and secondary outcomes, 6 months after the program has ended, will be evaluated for intervention group participants 12 months after randomisation.

Participants will be randomly allocated in equal numbers to:

- a) Immediate participation in the 6-month Active Women over 50 program (intervention group), n=500 or
- b) Delayed participation in the Active Women over 50 program, waitlist control (control group, n=500)

#### 4.2 Expected Duration of Study

The study is expected to take four years. We aim to recruit all 1000 participants within the first 3 years of the study. This will allow time to complete the 6-month, and optional 12-month, follow-up and data analysis within 15 months. Participant follow-up, data analysis and report writing will be completed within the 4-year grant timeframe, as outlined in Table 1.

**Table 1:** Trial timeline (n=1000) and recruitment plan

Task	Year 1	Year 2	Year 3	Year 4
Ethical approval, recruit staff, finalise intervention sites and procedures	✓			
Participants recruited in total (approx. 20/ week)	50	520	430	
Participants completed 6-month follow-up in total		400	400	200
Intervention group participants (n=500) completed optional 12-month follow-up in total		100	200	200
Data entry/ checking	✓	✓	✓	✓
Data analysis and manuscript draft completed.				✓

## 5. PARTICIPANT ENROLMENT AND RANDOMISATION

### 5.1 Recruitment

Advertising will be for the trial duration until 1000 participants have been recruited. We will advertise via the recruitment flyers and recruitment website. The recruitment flyer will provide the URL and a QR link to the recruitment website. The recruitment website will include the Participant Information Statement information. Advertising for trial participants will be undertaken through the general community via social media advertising and through community organisations, such as Arthritis NSW, the Council on the Ageing (COTA) NSW, and the Country Women's Association (CWA) of NSW and health promotion services that target women such as menopause services and BreastScreen NSW.

The recruitment flyers and website details will be distributed in newsletters, websites and social media (Facebook, LinkedIn and X (formerly known as Twitter)). The community organisations and promotion services will share the recruitment website and flyers on their social media accounts, website or in their newsletters. The recruitment website will have a link that will take potential participants to an online screening survey that will be hosted on REDCap on the University of Sydney server. The online screening survey will include the most up to date ethics approved Participant information Statement.

Advertising for trial participants will also be undertaken through online registries for research volunteers that enables volunteers to register their interest in taking part in ageing related research by a self-registration service. Registries will include *StepUp for Ageing Research* (<https://www.stepupforageingresearch.org.au/>) and *JoinUs* register (<https://www.joinus.org.au/>). Registries will be provided ethics-approved study documentation such as the ethics approval letter, trial protocol, participant information sheet, advertising flyers that contain the URL and a QR link to the Active Women over 50 study recruitment website. Registries will be requested to advertise the trial according to their privacy policy and will include but are not limited to StepUp for Research. StepUp for Research is an online self-registration service that enables volunteers to register their interest in taking part in dementia and/or ageing related research, either via StepUp for Dementia Research or StepUp for Ageing Research, respectively. The study team will only access the StepUp for Ageing Research component, and not the StepUp for Dementia Research component. The purpose of StepUp for Research is to allow such volunteers to be identified by researchers as potentially eligible for their studies. Researchers can then contact volunteers, in line with the volunteers' preferred method of contact, to discuss potential recruitment into a study. StepUp for Dementia Research was initially funded by the Commonwealth Department of Health and is delivered by the University of Sydney. StepUp for Research is not a research project but has been approved by the Human Research

Ethics Committee of the University of Sydney (project number 2018/680). The online service and all associated documentation, including methods of contacting volunteers and handling of data, were reviewed by a specially convened Governance Steering group within the University of Sydney which included experts in research ethics, data protection and information governance.

People who wish to participate will provide their contact details and consent for a member of the research team to telephone them to discuss their eligibility to participate. Prior assessing for eligibility, the research team will explain that the participant may require disclosing some personal information. Participants will be asked to provide verbal consent before they are asked some questions to confirm eligibility.

## **5.2 Eligibility Criteria**

### **5.2.1 Inclusion Criteria**

The trial will involve consenting adults who:

- Identify as a woman
- are aged 50 years and over
- live in the community across NSW
- do not meet the moderate-vigorous physical activity (MVPA) guidelines
- have access to an internet connected device
- want to receive support to be more active

### **5.2.2 Exclusion Criteria**

The trial will exclude adults who:

- have insufficient English language skills to fully participate in the program
- have a medical condition that precludes participation in regular physical activity
- have a cognitive impairment (a diagnosis of dementia or a Memory Impairment Screen score of less than 5)
- have a progressive neurological disease (e.g., Parkinson's disease)
- are unable to leave the house independently and walk 10 metres unassisted.

## **5.3 Study sites**

The trial will be conducted across urban, rural, regional, and remote areas of NSW.

#### **5.4 Informed Consent Process**

Potential participants will be provided with a participant information statement outlining the study procedures. The participant will have time to read the participant information sheet and discuss the study with family, friends and their local doctor if they choose to. Researchers at the University of Sydney will obtain online or written consent prior to any study commencement. After follow-up measures have been completed by the intervention group participants 6 months after randomisation, they will be provided with a second participant information statement. The statement will outline study procedures for participating in the follow-up study for an additional 6-months (ie., 12 months after randomisation). The participant will have time to read the participant information sheet and discuss their further involvement with family, friends and their local doctor if they choose to. Researchers at the University of Sydney will obtain online or written consent prior to any additional study participation. Participants will be made aware that the decision to participate will in no way influence any future decisions around their health care or any relationships with any organisations they have.

#### **5.5 Enrolment and Randomisation Procedures**

Participants will be enrolled into the study after initial screening to determine their suitability has been completed over the telephone, and having provided informed consent and completed all baseline surveys and device-based measurement of physical activity. Each participant will receive a study enrolment number, and this will be documented on all study documents. Group allocation will be determined using REDCap (Research Electronic Data Capture), a centralised web-based randomisation system within The University of Sydney with randomly permuted block sizes of four stratified by rural and urban locations. This will ensure concealment of allocation to groups and an auditable process.

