#### **5.6 Blinding Arrangements**

[figure not shown]
The primary outcome will be collected in a blinded fashion. Accelerometer device data will be processed and analysed by staff unaware of group allocation. All baseline measurements will be undertaken prior to group allocation. Due to the nature of the intervention being tested, full blinding of participants to intervention group allocation will not be possible. All reassessment survey collection will be undertaken by researchers blinded to group allocation. The additional 12-month follow-up measures (accelerometer device and survey) for the intervention group participants will not be undertaken by researchers blinded to group allocation.

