### 6.1.2 Health coaching

Participants will receive two health coaching sessions, lasting up to 60 minutes, delivered by telephone or videoconference as preferred by the participant. The health coach will be a tertiary-qualified physiotherapist or other health professional trained and experienced in delivering empowerment-focused coaching to facilitate physical activity behaviour change. The first coaching session will take place within 2 weeks of randomisation, and the second session four weeks after the first. This person-

centred health coaching approach will provide information and education. The sessions will also draw on evidence-based behaviour change techniques, practice and theories to help participants set goals, action plan, and provide accountability through prompting, monitoring and reinforcement. The coach's role is to work with participants to make achievable choices, reinforce and evaluate progress, and facilitate accountability.

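### A single printed block size of four would make up to one third of allocations certain to anyone who knows a stratum's history, so concealment is not ensured as the protocol states

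*Protocol*

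**What the plan says.** Protocol section 5.5 allocates through REDCap, described as "a centralised web-based randomisation system within The University of Sydney", using "randomly permuted block sizes of four stratified by rural and urban locations". It concludes that "This will ensure concealment of allocation to groups and an auditable process". Section 4.1 sets a 1:1 ratio: "Participants will be randomly allocated in equal numbers to" the two groups. No second block size appears anywhere; the plural in the phrase is slightly ambiguous, but the natural reading is a fixed block of four.

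The block size is not restricted information. Section 8.4.1 says the protocol will be peer reviewed and published, and section 5.1 lists it among the documents given to volunteer registries.

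On who can see allocations, section 5.6 accepts that "full blinding of participants to intervention group allocation will not be possible" but states that "All reassessment survey collection will be undertaken by researchers blinded to group allocation", and it also keeps the accelerometer processing staff unaware of group. In section 5.1 a research team member telephones volunteers about eligibility. In section 6.1.5 a research team member moderates a Facebook group that only women receiving the intervention may join. Under section 6.1.2, "The first coaching session will take place within 2 weeks of randomisation". Section 9.2 gives study staff role-dependent access to REDCap data, without mentioning allocation fields. The protocol does not say who triggers randomisation or whether that person can see earlier allocations.

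**The concern.** A central system hides the list of future allocations. It does not hide what past allocations imply about the next one. With a known block size of four, anyone who can follow a stratum in order knows where each block ends and can work out the remaining places. Here the size is printed, there are only two sequences to follow, and group membership is visible to some staff because one arm receives coaching and the other does not.

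What would be at stake is selection through timing. At the roughly 20 recruits a week in Table 1 (section 4.2), several women may be ready for randomisation together, and someone who knew the next arm could choose whom to randomise first. More motivated women could then collect in one arm. Adjustment for baseline steps (section 7.2) would not remove a difference in motivation.

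**Working it through.** **The plan's own figure.** The protocol gives no figure for predictability. Its only related number is the sample size in section 7.1: difference 1000 steps/day, SD 4200, 90% power, alpha 5% (taken as two-sided), 25% dropout.
- n per arm = 2 × (1.960 + 1.282)² × 4200² / 1000², which rounds up to 371.
- 371 / 0.75 gives 495 per arm, or 990 in total, in line with the stated 1000.

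This total is used below only to turn percentages into counts.

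**Inputs.** Block size 4, two strata and central allocation (section 5.5); ratio 1:1 (section 4.1). Assumption, not in the documents: the observer knows every earlier allocation in the stratum, in order.

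**Certain allocations, fixed block of four.** There are six balanced sequences. AABB and BBAA each leave two forced places; ABAB, ABBA, BAAB and BABA each leave one.
- Expected forced places per block = (2 × 2 + 4 × 1) / 6 = 1.33.
- Share = 1.33 / 4 = 33.3%, about 333 of 1000 under the full-knowledge assumption.
- By position: first 0%, second 0%, third 33.3%, fourth 100%.

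**Best-guess success, fixed block of four.** The chances of a correct best guess at positions one to four are 1/2, 2/3, 2/3 and 1. The third is (1/3 × 1) + (2/3 × 1/2) = 2/3. The mean is (1/2 + 2/3 + 2/3 + 1) / 4 = 70.8%, against 50% for an observer with no history.

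**Alternatives.** Fixed sizes were enumerated exactly. Varied sizes were simulated (200 runs of 500 allocations, sizes equally likely) for an observer who knows the full history and the set of possible sizes, but not the size of each block.

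| Scheme | Certain in advance | Best guess correct |
|---|---|---|
| Fixed 4 | 33.3% | 70.8% |
| Fixed 6 | 25.0% | 68.3% |
| Fixed 8 | 20.0% | 66.6% |
| Varied 4/6 | about 5% | about 69% |
| Varied 4/6/8 | about 2% | about 68% |

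Varying the sizes nearly removes certainty but moves best-guess success by less than three percentage points. Hiding the history removes both advantages, so access control matters at least as much as block size.

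**How fast allocations might become visible.** Coaching may start up to two weeks after randomisation. Table 1 gives about 20 recruits a week, although 520 in Year 2 is about 10 a week. Someone who learned allocations only from coaching could be 20 to 40 allocations behind, or 5 to 10 blocks of four over both strata. The high figure therefore needs someone who sees the REDCap result promptly.

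**The case against.** The strongest objection is that the high figure rests on access the documents do not describe. A reader might infer that one unblinded central team screens, randomises and books coaching, and so knows a third of allocations in advance. The protocol does not say this. It mentions research team members in several roles without saying they are the same people. It plans some separation, with blinded survey collectors and accelerometer processors, and it provides for role-based REDCap access. That part of the objection stands: one third is conditional. Section 9.2 does not settle the matter the other way, because it does not say that recruiting staff cannot see allocations.

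The route to bias is also narrow. Consent and all baseline measures precede allocation, so knowing the next arm cannot change baseline scores; what remains is the order in which women who are ready are randomised. The primary outcome is device-measured, processed blind and adjusted for its baseline value. This limits the likely harm, but blind processing protects measurement, not who enters each arm. No bias in steps per day has been estimated here, and the documents give no basis for one.

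Finally, fixed blocks of four with central allocation are a legitimate design. That is so, but the claim of ensured concealment goes further than the design supports.

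**Conclusion.** The point holds in a limited form. The protocol fixes one small block size in two strata, prints it in a document intended for publication, and claims ensured concealment without stating that recruiting or randomising staff are kept from past allocations. If they could see the ordered history of a stratum, up to 33.3% of allocations would be certain in advance and 70.8% of best guesses would be correct; both are worst-case values. If the history is hidden, the certain share falls towards zero. The documents do not show that allocations were or will be predicted, or that the estimate is biased. This is an inexpensive improvement to the design and a correction of wording, not an error that invalidates the trial.

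**What to change.** For any allocations still to be made:
- Load a REDCap table with block sizes varied at random (for example 4, 6 and 8) within the rural and urban strata.
- Keep the sizes with someone who takes no part in recruitment, and remove them from the circulated protocol.
- Set REDCap user roles so that staff who screen, take consent or trigger randomisation cannot view earlier allocations by stratum, and say so in section 5.5.
- Replace the statement that concealment is ensured with a description of the safeguards in place.

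The cost is one new allocation table, a change of user roles and some wording. The maximum imbalance within a stratum rises from 2 to 4 women (half of the largest block), negligible among 1000.

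Planned recruitment ran to December 2025, and the documents do not show how many allocations remain. Past allocations and past disclosure cannot be changed. If recruitment is complete, report the fixed block size, and who could see earlier allocations, as a limitation.

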#### **5.6 Blinding Arrangements**

[figure not shown]
The primary outcome will be collected in a blinded fashion. Accelerometer device data will be processed and analysed by staff unaware of group allocation. All baseline measurements will be undertaken prior to group allocation. Due to the nature of the intervention being tested, full blinding of participants to intervention group allocation will not be possible. All reassessment survey collection will be undertaken by researchers blinded to group allocation. The additional 12-month follow-up measures (accelerometer device and survey) for the intervention group participants will not be undertaken by researchers blinded to group allocation.

## 6 STUDY PROCEDURES SCHEDULE

Figure 1: Trial design

## 6.1 Intervention

The intervention group will receive access to the Active Women over 50 program. The Active Women over 50 program is a digitally delivered program designed with input from end-users across urban, regional and rural geographical settings and consists of four parts: 1) health coaching, 2) email or SMS behaviour change messages, 3) Active Women over 50 website, and 4) access to the Active Women over 50 private Facebook group.

